## Protocol Template Form

Item 1 UTHSCSA Tracking Number	HSC20150237H
-----------------------------------	--------------

Item 2 Abstract / Project Summary	Provide a succinct and accurate description of the proposed research. State the purpose/aims. Describe concisely the research design and methods for achieving the stated goals. This section should be understandable to all members of the IRB, scientific and non-scientific.  DO NOT EXCEED THE SPACE PROVIDED.
--	--

Purpose/Objectives: Frailty leads to poor health outcomes, such as falls, disability, hospitalization, institutionalization, and death. Diabetes is a significant predictor of the progression of frailty (e.g., gaining one or more frailty characteristic) in community-dwelling older adults ([name] et al., 2012). **Approximately 25-30% of older adults have diabetes and another 25-30% have glucose intolerance, a pre-diabetic state** (Kirkman et al., 2012). The major goal of this study to test a novel intervention strategy that could be used in the prevention of frailty in a sub-population of older adults who are at increased risk for becoming frail (those with pre-diabetes).

Aim 1: To determine whether the administration of metformin to glucose intolerant older adults reduces the onset or worsening of frailty.

Aim 2: To determine if the administration of metformin to glucose intolerant older adults reduces inflammation and improves insulin resistance.

Research Design/Plan: Randomized, double-blinded controlled trial of metformin vs. placebo for frailty prevention in older adults with pre-diabetes. This is a pilot study expected to be funded by the NIH-funded Older American Independence Center

Methods: Community-dwelling older adults  $\geq 65$  years will be randomized to metformin vs. placebo over a period of 2 years.

Clinical Relevance: The knowledge gained from this proposal will be the first to study a potential intervention targeted toward a central mechanism involved in the etiology of frailty. The results of this study could influence future clinical practice by suggesting that older pre-diabetic adults who are prescribed metformin will be less likely to become frail.

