c) Frailty assessment: Individuals identified as frail (approximately 10% of the community-dwelling older adult population) ([name] and Hazuda, 2008) will be excluded. Pre-frailty is defined as the presence of 1 or 2 of: 1) self-reported unintentional weight loss of 10 lbs or more in last year, 2) self-reported exhaustion, 3) low physical activity based on the Minnesota Leisure Time Physical Activity Questionnaire, 4) weak hand grip, 5) and slowness on 10-foot walk at usual pace. These measures have been standardized in SALSA, and will be used in this study as described ([name] and Hazuda, 2008). Non-frailty is defined as the presence of 0 characteristics. Frailty will be assessed every 6 months using the Fried criteria. If a participant's frailty category or score worsens based on Fried criteria (Fried et al., 2001), it will be repeated in 3 months and then at the 6 months intervals as per the protocol thereafter. At the baseline, self-reported unintentional weight loss will be used as criteria for weight loss as stated above. However, at all subsequent visits, individuals who have lost  $\geq 5\%$  of their baseline weight will be considered to have met the criteria for weight loss. As a measure of lower extremity function, we will use the Short Physical Performance Battery (SPPB) (Guralnik et al., 1994) and the 6-Minute Walk Test (6-MWT) (Harada et al., 1999). Both the SPPB and the 6-MWT are assessments of physical function commonly used in geriatrics studies. Lower extremity strength will be measured every 6 months with a knee extension dynamometer chair. The participants will be positioned in an upright position, with the ankle to a force or torque transducer at the knee angle of  $90^\circ$ . After 3 warm-up trials, 3 trials will be conducted to measure maximal voluntary contraction force of the knee extension muscle. We will also screen for depression using the Geriatric Depression Scale (Yesavage et al., 1982) and cognitive

impairment using the Mini Mental State Examination (Folstein et al., 1975) as part of the frailty assessment.

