i) Pharmacological intervention: After the baseline studies, subjects will be randomized to metformin (titrated up to 1000 mg twice daily, as tolerated) vs. placebo over a period of 6 months. Metformin and placebo are obtained from Major Pharmaceuticals (Livonia, MI). Randomization and drug preparation and dispensing will be performed by the Research Pharmacist of the BRU. Subjects will be initiated at 500 mg daily at Visit 2. Subjects will be seen in person at 1 week, and if tolerating metformin, will be directed to increase to 500 mg twice daily after 2 weeks. Phone calls will be made about every two weeks to titrate medications as tolerated as needed until patient is at maximum dose tolerated with goal dose of 1000 mg twice daily. At 3 months subjects will be seen in-person for a history & physical examination. OGTT will be performed every 6 months to monitor for diabetes conversion. Plasma metformin level will be measured once the participant has reached his/her maximum tolerated dose at either Visit 2, 4, 5, 6, 7, 8, 10, 11, 12, 13 or 14. If participants convert to diabetes and are started on metformin from placebo, an additional metformin level will be measured once the patient has reached his/her maximum tolerated dose at either Visit 2, 4, 5, 6, 7, 8, 10, 11, 12, 13, or 14. All patients will also receive patient education handouts about lifestyle modification to prevent diabetes at Visit 2.

j) Diet and exercise counseling: After the baseline visit, subjects will receive standard diet and exercise advice using resources available from the National Institute on Aging. This will be conducted by study staff member, [name], who is a certified diabetes educator. Resources will be given to subjects, including "Exercise & Physical Activity: Your Everyday Guide from the National Institute on Aging" available from <https://www.nia.nih.gov/health/publication/exercise-physical-activity/introduction>, and "What's On Your Plate? Smart Food Choices for Healthy Aging" available from <https://www.nia.nih.gov/health/publication/whats-your-plate>.

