**Follow up visits.** History/physical exam will be conducted every 6 months. Fasting glucose measurement and HbA1c will be conducted every three months, and OGTT will be conducted every 6 months. However, if fasting glucose and/or the HbA1c suggest conversion to diabetes based on American Diabetes Association criteria, OGTT will be performed. Assays of systemic inflammation (in plasma) will be conducted every 6 months. Insulin clamp with muscle biopsies will be conducted at 12 and 24 months, such that the treatment effect on tissue inflammation and insulin signaling may be determined. The table below outlines the follow up visits and procedures. A grace period of +/- 3 weeks is provided to complete follow-up visits.

Study visits and procedures															
Visit #	1	2	3	4	5	***6	7	8	9	***10	11	***12	13	14	15
Year	1												2		
Month	Screening Visit	0	1	3	6	9	12	12	12	15	18	21	24	24	24
Time Interval		3-21* Days	5-7 Days	2.5 Mo	3 Mo	3 Mo	3 Mo	3-21 Days	5-7 Days	2.5 Mo	3 Mo	3 Mo	3 Mo	3-21 Days	5-7 Days
History & Physical, with Frailty Assessment	X			X	X		X				X		X		
Biodex	*X				*X		*X			*X			*X		
Activity monitor		X							X						X
Quality of life assessment	X			X	X		X				X		X		
EKG	X						X								X
Urinalysis	X						X								X
OGTT	X				X		X				X		X		
Safety labs	X			X	X	X	X			X	X	X	X		
HbA1c	X			X	X	X	X			X	X	X	X		
Coagulation tests	X						X								X
Systemic inflammation		*X			X			*X			X				*X
DEXA		*X							*X						*X
Stool collection		*X							*X						*X
Insulin clamp w/ biopsy		*X							*X						*X
Examination of biopsy site			**X							**X					**X

\*These visits may be done at other approximate visits to reduce the amount of exposure to the participant due to COVID-19.

\*\*Due to COVID-19, the participants can opt to do this visit via phone or in person.

\*\*\*Due to COVID-19, if the participants do not need to do the Frailty assessment, this visit can be done via phone. Labs may be performed at the Quest Diagnostics laboratory nearest to the participant instead of the research unit.

**Urinalysis (UA) will be repeated if needed prior to starting on pioglitazone (only for subjects who convert to diabetes and do not have adequate glycemic control on metformin alone).**

**Basic metabolic panel (kidney function) will be performed as needed to check kidney function at least 48 hours after any radiologic exam using contrast dye.**

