**3.D.3. Power Calculation for Aim 1.** With 60 completers per arm, this study will achieve a power of 86% to detect an overall odds ratio of 0.20 for a one ordinal category increase in the frailty score in metformin versus placebo based on SAS **proc nlmixed** analyses of 1000 simulated databases with 6 repeated measures per subject, all subjects at frailty score 0 or 1 at baseline, an increasing random pattern in the placebo group, a pattern of lower frailty scores with increasing time on study in the treated group, and 10% of subjects in each arm remaining at baseline levels throughout all subsequent visits, two-sided testing, and a significance level of 5%.  At visits 1 through 6 Placebo subjects were assigned a 56% chance of increasing by one level, 22% staying the same, and 22% decreasing by one frailty level, and Treated subjects were assigned a 33% chance of increasing by one level, a 33% chance of staying the same, and a 33% chance of decreasing by one frailty level relative to the previous visit. With these parameter values, at baseline 50% of subjects were at frailty level 0 and 50% at level 1 in each arm and at visit 6 the distributions for Placebo were 0: 25%, 1: 22%, 2: 20%, 3: 18%, 4: 11%, 5: 4% on the average across the 1000 simulations. Distributions for Treated were 0: 50%, 1: 24%, 2: 14%, 3: 11%, 4: 0%, 5: 0% on the average across the 1000 simulations.

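### The frailty outcome has two assessment schedules, and the 86% power for Aim 1 matches the spacing of neither and does not reproduce from its own inputs

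*Combined protocol and SAP*

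**What the plan says.** - **Item 6, Screening Tests c), frailty assessment:** "Frailty will be assessed every 6 months using the Fried criteria". If the category or score worsens, "it will be repeated in 3 months and then at the 6 months intervals as per the protocol thereafter".
- **Item 6, Follow up visits (text):** "History/physical exam will be conducted every 6 months". It gives no separate frequency for frailty.
- **Study visits and procedures table:** the row "History & Physical, with Frailty Assessment" is marked at visits 1, 4, 5, 7, 11 and 13, which are screening and months 3, 6, 12, 18 and 24.
- **Item 6, Study Procedures i):** "At 3 months subjects will be seen in-person for a history & physical examination". This supports a month-3 visit but does not mention frailty.
- **Item 2:** participants "will be randomized to metformin vs. placebo over a period of 2 years".
- **3.D.3:** "With 60 completers per arm, this study will achieve a power of 86% to detect an overall odds ratio of 0.20", from "analyses of 1000 simulated databases with 6 repeated measures per subject". One set of per-visit probabilities is applied at each of visits 1 to 6: placebo 56% up, 22% same, 22% down; treated 33% each. Steps are defined relative to the preceding visit, with no interval length.

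**The concern.** Frailty progression is the Aim 1 outcome, and staff who follow the procedure text would not collect the month-3 measure that the table requires of everyone. The analysis tests a treatment-by-time interaction, so the number and timing of the measures are part of the primary test.

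The 86% is the only power figure given for Aim 1. If its simulated visits are not the trial's visits, it does not describe this trial. It is also unclear whether baseline is one of the six measures or whether six transitions follow baseline.

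**Working it through.** **1. Counting the measures.**

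| Source | Frailty months | Measures | Intervals (months) |
|---|---|---|---|
| Frailty text | 0, 6, 12, 18, 24 | 5 | 6, 6, 6, 6 |
| Visit table | screening, 3, 6, 12, 18, 24 | 6 | 3, 3, 6, 6, 6 |
| 3.D.3 | not given | 6 | equal steps |

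The conditional repeat does not explain the month-3 mark. On the text schedule the first post-baseline measure is month 6, so the earliest repeat is 6 + 3 = month 9. The COVID-19 footnote that lets a visit go by phone when no frailty assessment is needed attaches to visits 6, 10 and 12 (months 9, 15, 21), not to visit 4 (month 3).

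**2. Trying to reproduce 86%.** Inputs from 3.D.3: 60 per arm, baseline 50% at score 0 and 50% at score 1, 10% fixed at baseline, the transitions above, two-sided 5%. Assumption: scores are held within 0 to 5. Simulated power:

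| Course simulated | Adjacent-category mixed model, random intercept, treatment × time | Per-subject slope t-test |
|---|---|---|
| Baseline + 5 equal steps (6 measures) | 98.3% | 98.7% |
| Baseline + 6 equal steps | 98.7% | 99.6% |
| Visits 1 to 6 only, baseline not analysed | 93.7% | not run |
| Baseline + 4 steps (5 measures) | 96.4% | 97.7% |
| Five-step course, month 3 not measured | 98.0% | not run |
| Table months, half-size steps for 0–3 and 3–6 | not run | 97.2% |

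Monte Carlo error is about 0.4 to 1 point (somewhat more for the 93.7%, from 300 runs). With the three-category status in place of the 0–5 score, the mixed model gives 97% (six measures) and 96% (five). No variant comes near 86%, and the choice between five and six measures moves power by about 0 to 2 points.

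**3. Checking the printed visit-6 distributions.** For up, same and down probabilities u, s, d, the share at score j after step k + 1 is u·p(j−1) + s·p(j) + d·p(j+1), with moves beyond 0 or 5 held at the boundary. The final distribution is 0.1 × baseline + 0.9 × p. In per cent:

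| | Printed | 4 steps | 5 steps | 6 steps |
|---|---|---|---|---|
| Placebo, score 0 | 25 | 17.1 | 14.7 | 12.8 |
| Placebo, score 4 | 11 | 11.4 | 14.5 | 16.3 |
| Placebo, score 5 | 4 | 4.4 | 9.8 | 15.8 |
| Treated, score 0 | 50 | 38.9 | 36.7 | 34.8 |

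Printed means: placebo 0.22 + 2(0.20) + 3(0.18) + 4(0.11) + 5(0.04) = 1.80. Treated (0.24 + 2(0.14) + 3(0.11))/0.99 = 0.86. The separation is 1.80 − 0.86 = 0.94. The printed transitions give 0.91, 1.11 and 1.28 for four, five and six steps. No step count fits all cells. With other boundary rules and fixed shares of 0 to 20%, the best match found still misses a placebo cell by 5 points and a treated cell by 9.

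**4. When power falls below 86%.** This needs an effect that is not in the documents.
- Mixed model, arm difference scaled to 0.70: six measures 86.4%; month 3 omitted from the same course 85.6%; one whole transition removed 77.4% (error 1.5 to 2 points).
- Slope test, scaled to 0.73 so that five steps give 86%: four 6-month steps 80.5%; table with half-steps 79%.
- Slope test, scaled to 0.68 so that six steps give about 86%: about 74% on either schedule.

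**The case against.** The strongest reply is that this is a one-line consistency edit. The table and 3.D.3 agree on six measures, and because 3.D.3 ties a step to the preceding visit, not to elapsed time, a reader may take the simulation as matching the table. On the printed inputs, power exceeds 86% under either schedule. Five is also a minimum: the text adds repeats after worsening, and Study Procedures k) adds a frailty measurement at diabetes conversion. The printed arm separation (0.94) is closest to four steps (0.91), which is what 24 months of 6-monthly change would supply. The simulation code, random effects and tested contrast are not given, so no outside rerun can prove 86% wrong.

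Most of this stands. In particular, it rules out a reading that a reader might infer: that the schedule conflict means true power is below 86%, at about 74 to 80%. That range needs an effect shrunk to 0.68–0.73 of the printed difference and one step equated with 6 months. The documents state neither, and omitting month 3 alone costs about nothing.

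Three things survive the reply. The extra assessments fall only on participants who worsen or convert, so they cannot supply a sixth measure for all. Agreement on the count is not agreement on spacing, since the table's first two intervals are half the length of the rest. The six may not come from the frailty schedule at all: 3.D.5 also assumes six repeated measures for TNFα, although the Aim 2 design text plans plasma markers at baseline and every 6 months (five) and 3.D.4 at baseline, 12 and 24 months (three).

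**Conclusion.** The schedule conflict is documented: five measures in the frailty text, six in the visit table, with month 3 the difference. The 86% is not tied to either schedule's spacing and does not reproduce from its own inputs, which give about 96 to 99% in most variants and 94% in one. The printed visit-6 distributions and the printed transitions cannot both describe the same simulation under any setting tried.

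The documents do not show that the trial is underpowered, and the direction of the error in the 86% is open. These results rest on scores bounded at 0 and 5 and on two stand-ins for an unspecified nlmixed model. The point deserves correction because 3.D.3 holds the only power statement for Aim 1 and the correction is cheap.

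**What to change.** 1. Reconcile the frailty text, Study Procedures i), the Follow up visits text and the visit table into one list of frailty months. State whether month 3 applies to all participants, and keep the conditional repeats separate from the scheduled measures.
2. Rerun the 3.D.3 simulation on those months, with transition probabilities scaled to interval length and actual months as the time variable. State whether baseline counts as a measure, how scores at 0 and 5 are handled, the random effects and the tested contrast.
3. Replace the 86% and the printed visit-6 distributions with the results, whichever way they move.

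The cost is wording edits in a few places and one simulation rerun, with no extra patients or visits.

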
Older community-dwelling adults (age <math>\geq</math> 65 years) who are pre-diabetic
	
Inclusion criteria:
 
 
1) Men and women
 
2) All ethnic groups
 
3) Age 65 and older
 
4) Community-dwelling
 
5) Pre-diabetic based on oral glucose tolerance test (OGTT) with 2 hour values of 140 – 199 mg/dL after an oral glucose load, and no diagnosis of diabetes in the past 12 months
 
6) Subjects must have the following laboratory values: Hematocrit <math>\geq</math> 33%, aspartate aminotransferase (AST) <math><</math> 2 X upper limit of normal, alanine aminotransferase (ALT) <math><</math> 2 X upper limit of normal, alkaline phosphatase <math><</math> 2 X upper limit of normal, normal urinalysis (no clinically significant white blood cells, red blood cells, or bacteria), platelets <math>\geq</math> 100,000, PT <math><</math> 15 seconds and PTT <math><</math> 40 seconds, glomerular filtration rate [GFR] <math>\geq</math> 45
 
	
Exclusion criteria:
 
 
1) Characterized as frail, defined as the presence of 3 or more of: 1) weak hand grip strength, 2) slow walking speed, 3) low physical activity, 4) unintentional weight loss of <math>\geq</math> 10lbs over the past year, 5) self-reported exhaustion
 
2) Resident of nursing home or long-term care facility
 
3) Subjects with diabetes with range fasting glucose in diabetes range (<math>\geq</math> 126 mg/dL), or 2-hour glucose within diabetes range on OGTT (<math>\geq</math> 200 mg/dL),
 
4) Subjects taking drugs known to affect glucose homeostasis
 
5) Untreated depression or Geriatric Depression Scale (GDS) score on 15-item scale <math>></math> 7
 
6) Diagnosis of any disabling neurologic disease such as Parkinson's Disease, Amyotrophic Lateral Sclerosis, multiple sclerosis, cerebrovascular accident with
 

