#### Data Analysis Plan:

### STATISTICAL METHODS & POWER CALCULATIONS

**Overview.** In all analyses for Aim 1 and Aim 2, primary inference will be drawn based on intention to treat (ITT) analyses. Average complier effect (ACE) will be used to inform the metformin effect under full compliance to treatment assignments (Angrist et al, 1996). Per protocol analyses will be used to inform the metformin effect among completers. All analyses will be carried out unadjusted and with adjustment for covariates (Table 7) and covariate interactions with treatment and time. Corrections for multiple comparisons will be applied as appropriate.

The impact of metformin treatment on the progression of frailty status (non-frail, pre-frail, frail) over time will be assessed with a repeated measures mixed effects multinomial logistic model that models the log-odds of adjacent frailty statuses in terms of an indicator of metformin use, time, and the metformin use by time interaction. The possibility of non-linear trends of the log-odds of frailty statuses will be assessed by including an additional time factor (e.g., time squared) and its interaction with metformin use. The best fitting model will be used for inference. Secondary outcomes including gait speed, 6 minute walk, SPPB, frailty index constructed from the research data collected according to the Rockwood index (Searle et al., 2008; Rockwood et al., 2007), and body composition will similarly assessed. Under the linear trend model, the beneficial impact of metformin will be revealed by a significant time by treatment interaction associated with the log-odds of frailty status progression, indicating that the rate of increase in the likelihood of frailty progression over time is reduced in the metformin arm relative to the placebo arm. Under the non-linear trend model, the impact of metformin will be revealed by a significant reduction in the log-odds of frailty status progression in the metformin arm versus placebo at certain time points during the follow-up. SAS proc **nlmixed** will be used in the mixed effects model analyses. Proc **nlmixed** is preferred over other mixed effects modeling procedures such as GEE because it is valid under missing at random (MAR) assumption, accommodates linear and non-linear modelling, and uses maximum likelihood estimation.

Table 7. Covariates included in statistical analyses

Categories of covariates	Baseline	Time Varying
Demographics (age, sex)	X	
BMI (obesity), sarcopenia	X	X

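### As written, the follow-up frailty weight item counts any 5% loss, intended or not, so a subject who loses weight on purpose can gain a frailty point in the Aim 1 outcome

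*Combined protocol and SAP*

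**What the plan says.** Item 6, Screening Tests, c) Frailty assessment, gives the weight item two definitions.

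- Entry: "At the baseline, self-reported unintentional weight loss will be used as criteria for weight loss as stated above". This is a self-report of losing 10 lb or more in the past year. Exclusion criterion 1 in Item 5 also carries the intent condition ("3) low physical activity, 4) unintentional weight loss of" at least 10 lb).
- All later visits: a subject who has lost 5% or more "of their baseline weight will be considered to have met the criteria for weight loss". Intent is not mentioned.

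If category or score worsens, the assessment is redone: "it will be repeated in 3 months and then at the 6 months intervals as per the protocol thereafter". The row "History & Physical, with Frailty Assessment" in the visit table places assessments at screening and at months 3, 6, 12, 18 and 24.

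The Study Procedures section supplies a reason for intended loss. Under i): "All patients will also receive patient education handouts about lifestyle modification to prevent diabetes at Visit 2". Under j): "After the baseline visit, subjects will receive standard diet and exercise advice using resources available from the National Institute on Aging".

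The Overview of the statistical methods makes the three-level status the Aim 1 outcome: "The impact of metformin treatment on the progression of frailty status (non-frail, pre-frail, frail) over time will be assessed". A two-point rise in the score is one component of the major adverse outcome (3.D.6), and an increase in the score is the outcome related to insulin sensitivity and inflammation in Aim 2 (3.D.4).

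**The concern.** A subject who takes the advice, loses 5% of baseline weight on purpose and keeps it off scores one point for weight at every later assessment. The 3-month repeat applies the same rule, so it does not remove the point. A response to the advice is then recorded as a step towards frailty.

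Three analyses use the item. Aim 1 status can move from non-frail to pre-frail, or from pre-frail to frail. For the two-point adverse outcome, one further item is then enough. In Aim 2, the background section attributes insulin resistance in ageing partly to adiposity and inactivity. The same subject could therefore gain insulin sensitivity and a frailty point together, against the association that Aim 2 sets out to test.

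The two definitions also differ in source, look-back and threshold: 5% equals 10 lb only at 10/0.05 = 200 lb. A subject positive at entry only through past-year loss drops the point at follow-up unless a further 5% is lost. Randomisation balances this mismatch between arms, so it is secondary.

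**Working it through.** **1. When the point matters.** Let k be the total of the other four items, and suppose the weight item was not met at entry. The score goes from k to k+1. With cuts at 0, 1–2 and 3 or more, status changes only if k = 0 or k = 2. A subject who already met the item at entry gains no net point.

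**2. Starting distributions.** The documents give no rate of intended loss, so every share below is assumed. 3.D.3 states these visit-6 scores (0 to 5):
- Placebo 25/22/20/18/11/4%: non-frail 25%, pre-frail 22+20 = 42%, frail 18+11+4 = 33%.
- Treated 50/24/14/11/0/0%, which sums to 99% and is rescaled: 50/99 = 50.5%, 38/99 = 38.4%, 11/99 = 11.1%.

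The model is log(p_{j+1}/p_j) = a_j + b × treated, with one common b fitted to the expected proportions. This gives exp(b) = 0.415. Mean category (0, 1, 2) is 1.080 against 0.606, a difference of 0.474.

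**3. Equal share w in both arms, independent of score.** Those who move up are w × (25% + 20%) = 0.45w of placebo and w × (50 + 14)/99 = 0.646w of treated, with 60 per arm.

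| w | Moved, of 120 | Odds ratio | Mean difference |
|---|---|---|---|
| 0 | 0 | 0.415 | 0.474 |
| 5% | 1.35 + 1.94 = 3.3 | 0.422 | 0.464 |
| 10% | 2.70 + 3.88 = 6.6 | 0.428 | 0.454 |
| 20% | 5.40 + 7.76 = 13.2 | 0.437 | 0.435 |

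**4. Relaxing the assumptions.**
- Some already hold the item (a fraction k/5 of those at score k): odds ratio 0.420, 0.424 and 0.430. At 20% the mean difference is 0.430, below the 0.435 in the table, so the table is not a bound.
- An equal 10% of each arm, all at score 0: 6 + 6 = 12 move. Placebo becomes 15/52/33% and treated 40.5/48.4/11.1%. The odds ratio is 0.352, away from 1, while the mean difference stays at 0.474.
- Unequal shares: 20% metformin and 5% placebo gives 0.502; 5% and 20% gives 0.367.

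**5. Closer to the planned model.** The transition probabilities in 3.D.3 were simulated with 60 per arm, scores held within 0–5 and 10% non-changers. A random-intercept adjacent-category logit was fitted, with 100 runs per scenario (Monte Carlo error about 3 to 5 points). With baseline plus six visits, the overall treatment test has 85% power against the plan's 86%. With baseline plus five visits, as in the visit table, an extra weight point was then added at every follow-up visit for a share of each arm:
- Overall test on the 0–5 score: 89% with no extra points, and 84% at 10% in both arms.
- Overall test on three-level status: 93%, then 90%.
- With 10% placebo and 40% metformin, the overall test falls to 52% (score) and 33% (status).
- The time-by-treatment test stayed at 92–100% in every scenario.

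The transitions in 3.D.3 do not reproduce its visit-6 distributions: six exact steps give placebo 13/18/18/19/16/16%. Steps 2–4 and step 5 are therefore separate illustrations.

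**The case against.** *Citing the Fried criteria may imply intent.* This does not settle it. The background and preliminary-data sections call the item simply weight loss, and the specific sentence on later visits contrasts itself with the entry rule. If intent was meant, the text still needs to say so for assessors to score alike.

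*The planned test is hardly affected.* This largely stands. Under the linear-trend model, benefit is read from the time-by-treatment interaction, whose simulated power held up. The limits are that the non-linear version and the interaction's type I error were not examined, and that the simulation added the point from the first follow-up visit, not gradually.

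*Other measures compensate.* Partly. Gait speed, 6-minute walk and SPPB do not use the item, a separate frailty index is planned, and time-varying BMI is a listed covariate. None of these re-scores the Aim 1 category.

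*Measured weight is more objective than stated intent.* This stands. Intent asked after randomisation may be coloured by a guess at allocation. Under k) Management of conversions, allocation is unblinded in diabetes converters. The COVID-19 footnotes suggest that the trial is under way, so completed visits would lack the answer. Intent should therefore not redefine the primary score.

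A reader might infer that the rule biases the trial against metformin. The documents do not support that: the handouts go to all patients, the counselling is not tied to arm, and nowhere do they say that metformin changes weight. Gastrointestinal reactions are listed as common, but a link from these to a 5% loss is inference. A reader might equally infer that equal shares can only dilute the effect; the score-0 case in step 4 shows otherwise.

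**Conclusion.** The point holds as a matter of text: no passage restores the intent condition after baseline, so a sustained intended 5% loss counts as frailty for a subject not already positive on the item. The harm is modest misclassification and does not threaten the trial. Under assumed equal shares of 5% to 20%, independent of score, it affects about 3 to 13 of 120 completers at visit 6 and shifts a cross-sectional odds ratio from 0.415 to between 0.422 and 0.437. These figures are illustrations, not limits, and the cross-section is not the planned mixed model. The direction is not assured even with equal shares. The larger effects need a difference in weight loss between arms that the documents do not indicate. The case for acting is interpretability at low cost.

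**What to change.** 1. Keep the measured 5% item in the primary score, so that one follow-up rule applies to completed and future visits alike.
2. Pre-specify a sensitivity analysis of the Aim 1 model and the two-point component with the weight item removed at both baseline and follow-up: status cut at 0, 1–2, and 3 or more of four items, and the two-point rise taken on the 0–4 score.
3. From now on, record at each frailty visit whether a 5% loss was intended. Pre-specify a second sensitivity analysis that scores the item only for unintended loss where intent was recorded.
4. State in advance that all results will be reported.

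The cost is one question per frailty visit and a wording change; the four-item analysis uses data already collected. There are three downsides. Intent is self-reported after randomisation, possibly after unblinding in converters, and is missing for completed visits. The question does not remove any drug-related loss, which only the four-item analysis addresses. Three of four items is harder to reach than three of five, so that analysis compares arms and does not estimate the five-item frailty rate.
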